#### **Data Use Agreements:**

Version 04/23/2018

For this analysis, we will enter into three data use agreements in order to complete our secondary data analysis aims. We will enter into a Data Use Agreement with the Office of GEC for the use of the ADNA assessments and The Lewin Group readiness assessments both of which are reported to GEC as part of routine care/service. Only the ADNA Assessments contain PHI. The second data use agreement will be with the VA Caregiver Support Program. The caregiver survey data will be used as a comparison group for our research analysis of the Caregiver Survey (Objective 2). Finally, we will enter into a data use agreement with PEPReC for the VD-HCBS program analysis data including VAMC randomization criteria, the utilization outcomes analysis, and the economic outcomes analysis data. This will allow us understand the context of implementation in programs that are 'successful' in implementation and outcomes development of VD-HCBS.

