## Recruitment Methods:

This objective will be completed in two separate stages. The first stage will be data collection of caregiver Survey data via telephone surveys. Caregivers of Veterans receiving VD-HCBS will be given a sealed packet during the ADNA's initial visit or will be placed within the Veteran interview packet to be mailed as described above. The sealed packet will be labeled "To the Veteran Caregiver" and will include information about the project, the phone survey, the goal of the project, and provide contact information of a Providence-based project staff member to address any questions or concerns they may have prior to participating. Also included in these letters will be a copy of the informed consent sheet for caregivers to keep and will contain contact information should they have any questions either before or after the survey. In addition, within this introductory packet will be an opt-in postcard that caregivers will be asked to complete and return if they wish to participate or be contacted again regarding this study. A draft of this opt-in postcard is included in the application (Opt-in Postcard included in submission). . Data for the outcomes for caregivers of Veterans enrolled in the VD-HCBS program will be obtained from the VHA Office of Geriatrics and Extended care following an approved Data Use Agreement in accordance with VA Policy. We estimate that there will be approximately 4500 Caregivers' data included in this data set. Data for the control group will be obtained from the VHA Caregiver Support Program following an approved Data Use Agreement in accordance with VA Policy. We estimate that there will be approximately 158 Caregivers (92 approved for the Caregiver Support Program and 66 not approved) with pre and post survey data included in this data set.

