In order to compare the VD-HCBS Caregivers to the control group of Caregivers from the VA CARES evaluation (non-approved Caregivers, n=66), we will attempt to identify VD-HCBS Caregivers that are similar to the control group participants in terms of baseline survey variables. Identifying matching individuals on the entire set of covariates may be complex, so we will rely on the propensity score, a technique used in non-randomized studies to balance groups based on observed differences. Because the number of participants in our control group is significantly smaller than the one expected in VD-HCBS, we will use matching with replacement in which controls can be used multiple times to match within a specified caliper. Caregivers in VD-HCBS that will not have a matching VA CARES within a caliper will be removed from the analysis, because the positivity assumption does not seem to be valid for them. This procedure will include many Caregivers in VD-HCBS, which will improve the precision of point estimates in this group while maintaining only VD-HCBS Caregivers that are relatively similar to control Caregivers. Having a large number of Caregivers from VD-HCBS increases the power of the study, but it is dominated by the precision in the control group. To estimate the propensity score, we will use a logistic regression model  $P(C_i|X_i) = \frac{\exp(\beta'X_i)}{1 + \exp(\beta'X_i)}$ , where Ci is indicator variable for whether Caregiver i is from the VD-HCBS program or the control group, and Xi are the set of baseline covariates for caregiver i. Following the propensity score calculation, we will match Caregivers in the control group to VD-HCBS Caregivers using the estimated propensity scores. We will then examine whether the distributions of the baseline covariates and second order interactions are similar across the two groups. Differences in distributions will be examined graphically and via appropriate statistical tests. If some variables are found to differ between groups, we will update the propensity score model with higher order interactions. We will repeat this procedure until balance is obtained on all baseline variables and their interactions. 40

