esponses are "Poor", "Fair", "Good", "Very Good" or "Excellent"								
line items assessing positive aspects of caregiving as captured by								
arlow and colleagues' reliable and well-validated measure.								
cores range from 9-45 where higher indicates more positive aspects								
f caregiving experienced.								

Caregivers and a few will be drawn from the Veteran Assessment Data. For example, the models will include Veterans' demographic and health/function characteristics, month of enrollment, and the Veterans' monthly budget amount. We will also examine Caregiver characteristics such as their relationship with the Veteran, whether or not the Caregiver was employed, lived with the care recipient, as well as their age, sex, race, education, marital status, and whether or not there are dependent children in the household.

Power-

Without any adjustment for covariates and assuming that the standard error is equal to

Estimated Power for Aim 2 Caregiver Analysis by Effect Size and Number of Surveys											
VD- HCBS	5120 0110	Effect Size									
Caregiver Surveys	3 pts	3.5 pts	4 pts	4.5 pts							
(n)	P13	pts	pt3	pts							
500	56%	70%	80%	89%							
1,000	58%	71%	82%	90%							
2,000	59%	73%	83%	91%							

10 (the observed standard deviation on the Positive Aspects of Caregiving Scale in the non-approved "control group" from the VA Cares evaluation, n=55 respondents for this scale), we should have over 80% power to identify a difference of 4 points on the Positive Aspects of Caregiving Scale (range 9-45) with approximately 1,000 Caregivers in VD-HCBS (see Table 4). If we used a

different control group, (i.e., the approved Caregivers in the VA CARES evaluation, n=92 respondents), we can identify a 3.1 point difference on this scale. Using regression adjustments, we are expecting to be able to identify even smaller effects. Therefore, we expect to have a large enough sample size to detect a meaningful difference in at least one of the outcomes for this objective

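### Controls are limited to caregivers not approved for the Caregiver Support Program, but the available text sets no such limit for VD-HCBS caregivers and does not name approval as a covariate

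*Combined protocol and SAP*

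**What the plan says.** The control side is defined by a second program. Section 5.0 (Objective 2, Recruitment Methods) expects data on "approximately 158 Caregivers (92 approved for the Caregiver Support Program and 66 not approved"), and section 7.0 (Objective 2) names the comparison group as the "control group of Caregivers from the VA CARES evaluation (non-approved Caregivers, n=66").

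The VD-HCBS side is defined only by the Veteran's enrolment: "Caregivers of Veterans receiving VD-HCBS will be given a sealed packet during the ADNA's initial visit", or receive it inside the mailed Veteran interview packet, and they opt in by postcard. The recruitment and consent text for Objective 2 contains no screen or exclusion on Caregiver Support Program status.

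On matching, section 7.0 says: "we will attempt to identify VD-HCBS Caregivers that are similar to the control group participants in terms of baseline survey variables". The named model covariates in section 7.0 are:

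- baseline values of the outcomes;
- Veteran demographics and health or function;
- month of enrolment and monthly budget;
- a set of caregiver items: "We will also examine Caregiver characteristics such as their relationship with the Veteran, whether or not the Caregiver was employed", co-residence, age, sex, race, education, marital status and dependent children.

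Approval status is not named. The approved caregivers (n=92) appear in the analysis section only as a possible alternative control group in the power paragraph.

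**The concern.** The plan treats approval as a distinction that matters: it splits the VA CARES caregivers by it and takes the non-approved group for the planned comparison. The visible text does not carry the distinction over to the VD-HCBS arm. The Caregiver Support Program could act on the outcomes that Objective 2 tests, namely financial strain, depressive symptoms, burden, health and positive aspects of caregiving. If some VD-HCBS caregivers are approved for it and no control was approved at entry, the treatment coefficient tau in section 7.0 estimates VD-HCBS plus some share of the other program. A reader of the result could not separate the two, and without a record of approval nobody could say whether the problem was large or negligible.

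**Working it through.** **Inputs from section 7.0, Objective 2 (Power).** SD 10 on the Positive Aspects of Caregiving Scale; 55 non-approved controls with data on that scale; about 1,000 VD-HCBS caregivers; target difference 4 points. Alpha is not stated there; two-sided 5% is assumed.

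**Step 1. Reproduce the plan's figure.**

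SE = 10 × √(1/55 + 1/1,000) = 1.385.

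Power for 4 points = Φ(4/1.385 − 1.96) = Φ(0.928) = 82.3%, against a stated 82%.

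With 500 VD-HCBS caregivers, SE = 10 × √(1/55 + 1/500) = 1.421 and power is 80.4%, against a stated 80%. The power table is not in error. It simply does not address bias.

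**Step 2. Bias from overlap.** Let f be the share of matched VD-HCBS caregivers who are approved, and e the effect of the Caregiver Support Program on the change score over follow-up. With no approved controls, bias in tau = f × e. Neither f nor e is in the documents. The assumed ranges are f = 0 to 40% and e = 2 to 4 points.

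**Step 3. Rejection rate when VD-HCBS has no effect.** This is Φ(b/1.385 − 1.96) + Φ(−b/1.385 − 1.96), where b is the bias.

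| Overlap f | Bias, e = 2 | Rejection | Bias, e = 4 | Rejection |
|---|---|---|---|---|
| 0% | 0 | 5.0% | 0 | 5.0% |
| 10% | 0.2 | 5.2% | 0.4 | 6.0% |
| 20% | 0.4 | 6.0% | 0.8 | 8.9% |
| 40% | 0.8 | 8.9% | 1.6 | 21.1% |

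Only the corner with 40% overlap and a 4-point effect exceeds 9%. That effect equals the plan's whole target difference.

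**Step 4. Direction.** The outcome is change from baseline, and baseline values enter the models. If approval comes after baseline and the program helps, e is positive and the bias favours VD-HCBS. If approval came well before baseline, the benefit is already in the baseline score; e may then be near zero, or negative if less room to improve remains.

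**Step 5. Cost of restricting.** At 40% overlap, 600 of 1,000 VD-HCBS caregivers remain: SE = 10 × √(1/55 + 1/600) = 1.409, and power for 4 points is Φ(4/1.409 − 1.96) = 81%. The controls limit precision, as section 7.0 itself says.

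**Limits of the calculation.** It covers one scale. It uses the plan's simple SE; matching with replacement reuses controls and may enlarge the SE, which would lower the rejection rates but leave the bias unchanged.

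**The case against.** The strongest reply is that this argues from silence. The covariate text is illustrative rather than closed, the survey items are not shown, and the abstract describes the caregiver survey as aligned with the Caregiver Support Program, so a status item is plausible. Part of the protocol between section 3.0 and the Data Use Agreements paragraph was not available and could contain eligibility rules. The documents also do not say whether a caregiver can be in both programs. All of this stands, and it limits the point to what the visible text commits to.

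Three stronger readings are tempting, and the documents support none of them.

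- **That the estimate is biased toward the hypothesis.** Overlap and effect are unknown, and the direction turns on the timing of approval.
- **That matching cannot repair the problem.** Section 7.0 states that "Caregivers in VD-HCBS that will not have a matching VA CARES within a caliper will be removed from the analysis". If approval were recorded and entered in the propensity model, approved VD-HCBS caregivers would have no comparable control and that rule would remove them. The gap is an unnamed variable, not a failure of the method.
- **That controls received no caregiver support.** The text says only that they were not approved. It does not say that they stayed so during follow-up or had no other support.

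A reader might also ask whether some controls' Veterans were themselves in VD-HCBS, since the Significance section says that 51 VAMCs offer it. That would dilute the contrast. But nothing shows that the VA CARES file holds this information, and excluding controls would shrink the group that limits precision.

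**Conclusion.** The point holds as a gap in the visible plan with a conditional consequence. A condition placed on the controls is not placed on the VD-HCBS arm, and the status that defines it is not a named covariate. If there is co-enrolment, tau mixes two programs. Under the assumed ranges the bias runs from 0 to 1.6 points against a 4-point target, with rejection of 5% to 21% when VD-HCBS does nothing; most of that range lies at or below 9%. With little overlap, or approval well before baseline, the bias may be negligible. The point warrants a cheap improvement to the plan. It does not show that the comparison is invalid.

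**What to change.** 1. Add one item on Caregiver Support Program approval or receipt to the baseline and follow-up telephone surveys of VD-HCBS caregivers. If such an item already exists, name it in section 7.0.
2. Restrict the matched comparison to VD-HCBS caregivers not approved at baseline. Stating the restriction outright is cleaner than relying on the caliper, because approval would perfectly predict group membership among approved caregivers and unsettle the logistic model.
3. Report the all-caregiver result as a sensitivity analysis, with a further one that excludes caregivers approved during follow-up. The latter conditions on a post-baseline event and should stay a sensitivity analysis.
4. Check whether controls' Veterans were in VD-HCBS only if the VA CARES data already allow it.

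The survey item is preferable to seeking status by data linkage. The relevant agreement ("The second data use agreement will be with the VA Caregiver Support Program") is described as supplying comparison-group data, and the consent waiver requested for Objective 2 covers the control group.

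The cost is one item in each survey and a small loss of precision: 4-point power goes from about 82% to 80% even if the VD-HCBS caregivers fall from 1,000 to 500. One weakness remains. If the controls applied and were declined, VD-HCBS caregivers who never applied are not in quite the same position, so the plan should state what not approved means in the VA CARES data.

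### Statistical tests are a poor stopping rule for propensity balance with 66 reused controls, and the refit loop has no numeric limit, cap or fallback

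*Combined protocol and SAP*

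**What the plan says.** Section 7.0, Objective 2, takes as its comparator the 66 VA CARES caregivers who were not approved for the Caregiver Support Program. "Because the number of participants in our control group is significantly smaller than the one expected in VD-HCBS, we will use matching with replacement", with a caliper whose width is not given. VD-HCBS caregivers without a control inside the caliper are dropped.

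After matching, baseline covariates and their second-order interactions are compared between groups. "Differences in distributions will be examined graphically and via appropriate statistical tests". If variables differ, higher-order interactions are added to the logistic propensity model. The end point of the process is: "We will repeat this procedure until balance is obtained on all baseline variables and their interactions".

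The text names no test and no significance level. It gives no limit for a standardised mean difference (SMD) or variance ratio, and no rule for whether tests allow for reused controls. It sets no cap on refits and no minimum effective number of controls, and it does not say what happens if balance is never reached.

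Two later safeguards belong to the picture. The primary comparison is change from baseline to follow-up. The imbalances that remain after matching, which the plan expects to be minor, are handled by regression on the covariates, including the baseline value of each measure.

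**The concern.** A test result mixes the size of an imbalance with the amount of information available to detect it. Bias depends only on the size. With few controls, an imbalance that matters can be non-significant. With replacement, some controls are used many times and others hardly at all, so the effective number can be well below 66. If the tests reflect that, a refit that concentrates the matches on fewer controls makes every test easier to pass.

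If the tests ignore reuse, the opposite happens: trivial differences are flagged and the loop keeps refitting. Each refit adds terms to a logistic model whose smaller group has 66 members, which invites overfitting and separation.

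The stake is the Objective 2 effect estimate. The rule could leave confounding in the matched sample, use up the control information on which precision mainly depends, or fail to end.

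**Working it through.** **Inputs.** All come from Section 7.0, Objective 2, unless marked as assumed.
- Controls: 66 in the non-approved group; for the powered scale, "n=55 respondents for this scale".
- VD-HCBS caregivers: the power statement is made "with approximately 1,000 Caregivers in VD-HCBS".
- SD 10 points, target difference 4 points.
- Assumed: two-sided 5% tests, since no level is stated.
- Assumed: effective control counts of 33 and 20, since none is given.

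**1. The plan's own power figure.** The standard error is 10 × sqrt(1/55 + 1/1000) = 1.385. Power for 4 points is Φ(4/1.385 − 1.96) = Φ(0.93) = 82%, as in the power table. The whole table reproduces to within 2 percentage points with 55 controls at full weight, and not with 66. It therefore contains no allowance for loss through reuse.

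**2. Tests that reflect the controls actually used.** The largest SMD that passes is 1.96 × se, with se = sqrt(1/n + 1/1000), where n is the distinct or effective number of controls. A true SMD of 0.20 passes with probability Φ(1.96 − 0.20/se) − Φ(−1.96 − 0.20/se).

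| Controls n | se | Largest SMD that passes | Chance that an SMD of 0.20 passes | Power for 4 points |
|---|---|---|---|---|
| 66 | 0.127 | 0.25 | 65% | 88% |
| 55 | 0.138 | 0.27 | 70% | 82% |
| 33 (assumed) | 0.177 | 0.35 | 80% | 62% |
| 20 (assumed) | 0.226 | 0.44 | 86% | 43% |

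The number of VD-HCBS caregivers hardly matters: with 66 controls the limit is 0.257 at 500 and 0.245 at 2,000. The power column ignores regression adjustment, which the plan expects to help.

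**3. Tests that treat matched rows as independent.** With 1,000 rows on each side the limit is 1.96 × sqrt(2/1000) = 0.088, whatever the degree of reuse.

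**4. Requiring every term to pass.** The plan lists 5 outcome measures, whose baseline values enter, and 9 caregiver characteristics: relationship, employment, co-residence, age, sex, race, education, marital status and dependent children. That is 14 main effects and 14 × 13/2 = 91 two-way terms, 105 in all. Veteran characteristics would add more. Under true balance at 5%, 105 × 0.05 = 5.25 false flags are expected. If the tests were independent, all would pass with probability 0.95^105 = 0.0046, about 0.5%.

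**5. Illustrative simulation.** Assumed: 10 or 15 normal covariates, 1,000 against 66, caliper 0.2 SD of the logit, shifts of 0 to 0.3 SD per covariate. Effective controls averaged between about 39 and 20. With tests based on effective controls, all main effects passed in 87–100% of runs, although the mean worst SMD was 0.18–0.36. With matched rows taken as independent, all main effects passed in at most about 3% of runs. The two readings thus fail in opposite directions. The 0.5% in step 4 is a reference value for tests that keep their nominal error rate. Matching can make tests of the first kind pass more often than that, so a loop that does not end is mainly the risk of the second kind.

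**The case against.** The strongest reply is that the plan leaves its criterion open rather than adopting a bad one. Graphs are used as well as tests, and no p-value threshold appears. A reader might infer that balance is judged by 5% significance tests alone; the text does not say that. What can be said is that the tests are the only part of the check that yields a yes/no answer, and that the missing-data paragraph of the same section does decide by whether differences are significant. The 5% level here remains an assumption.

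A reader might also infer that the rule necessarily accepts large imbalance and rewards the loss of controls. That follows only if the tests reflect distinct or effective controls. Tests on matched rows are stricter (0.088) than a target of 0.1. The documents do not say which applies, so neither direction of failure is established.

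A third inference would be that the matched comparison alone carries the Objective 2 effect, so that an SMD of 0.27 on the SD-10 scale, or 2.7 points, could be set against the 4-point target as bias. That is not supported. The outcome is change from baseline, the regression adjusts for baseline values, and interval estimates are planned by the Abadie–Imbens variance or the bootstrap. A baseline imbalance does not pass one-for-one into the effect.

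These points narrow the concern but do not remove it. The regression is written with covariates entering linearly and no interactions shown, although the balance check itself treats interactions as needing balance. Nothing in the loop ensures that only minor imbalances reach the regression.

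**Conclusion.** The concern holds in this form: the stopping rule rests on unspecified tests that are unsuited to 66 reused controls, and it has no numeric limit, cap or fallback. If the tests count distinct or effective controls, SMDs up to 0.25–0.27 pass at the stated control numbers and up to 0.44 at an assumed 20, so losing controls makes passing easier. If they count matched rows, the limit is about 0.09 and the loop may not end.

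This is more than missing detail, because either natural reading of the rule works badly. The size of any bias in the final estimate cannot be derived from the documents, and the planned change comparison and regression adjustment will reduce it. The figures rest on two-sided 5% tests, 1,000 VD-HCBS caregivers, assumed effective control counts below 55, and independence of the 105 terms. Whether an SMD of 0.25 is large is a judgement for which the documents give no benchmark.

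**What to change.** Change the balance paragraph in Section 7.0, Objective 2, as follows.
- Replace the tests with SMDs weighted by how often each control is used, add variance ratios, and keep the graphs.
- State a target in advance, for example an SMD of 0.1, as a goal and not as a condition that must be met.
- Limit the propensity model to a number of terms that 66 controls can support, or use a penalised score or covariate-balancing weights.
- Cap the number of refits and carry them out without access to follow-up outcomes. The plan does not propose to use outcomes here, but the control follow-up data already exist (Section 5.0, Objective 2, Recruitment Methods).
- Report the effective number of controls, (Σw)²/Σw², where w is the number of times each control is used.
- If the target is not met, report the remaining imbalance and rely on the regression adjustment already planned.

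The cost is SAP wording only. The downside is that several terms may stay above 0.1 and must be reported. With 66 controls at full weight the SMD has a standard error of 0.127, so a single truly balanced term falls within 0.1 only about 57% of the time before any gain from matching (2Φ(0.1/0.127) − 1). That is why the target should be a goal with a fallback.
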